3 STUDY OBJECTIVES

The following key definitions are provided as a reference for understanding the study objectives and are used throughout the protocol.

Sustained remission is achieved when a subject has an ASDAS <1.3 at Week 32 or Week 36 (if ASDAS <1.3 at Week 32, it must be <2.1 at Week 36 [or vice versa]) and at Week 48. A subject is eligible for Part B of the study only if sustained remission is achieved in Part A.

A flare occurs when a subject has an ASDAS ≥ 2.1 at 2 consecutive visits or ASDAS >3.5 at any visit during Part B.

Subjects who meet the criteria of flare during Part B and who crossed-over to full-dose treatment (CZP 200mg Q2W) are regarded as escapers.

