ⁱ Screening chest x-ray must have occurred within 3 months prior to Screening or during Screening, and should be repeated only if the TB test was confirmed positive or any further evidence is suggestive of potential TB infection (eg, exposure).

^j QuantiFERON TB GOLD test or another WHO-validated IGRA test such as Elispot test, if QuantiFERON TB GOLD test is not locally available. The TB test will be repeated at Week 48 and 96 (or at WD Visit if medically indicated) for subjects with previously negative TB test result.

^k Sacroiliac joint x-rays will be performed at Screening and used as the Baseline assessment for all subjects. An SIJ x-ray performed \leq 12 months prior to the Baseline Visit may be used as the Baseline assessment provided that the film can be submitted and meets the requirements for central reading.

^l Magnetic resonance imaging of the spine and sacroiliac joints to be performed at Screening, and within a \pm 2 weeks time window at Weeks 48 and 96 or WD Visit if the last MRI was performed more than 12 weeks prior to WD Visit.

^m Kit for collection of stool sample to be provided at Screening Visit. Stool sample shall be obtained prior to Baseline and provided to the Investigator at the Baseline Visit.

ⁿ Occiput to wall distance; chest expansion; and BASMI, which includes modified Schober test, lateral spinal flexion, cervical rotation, tragus to wall distance, and maximal intermalleolar distance.

^o Resource utilization includes: concomitant medical procedures, health care provider consultations not foreseen by the protocol, hospitalizations/emergency room visits.

^p Prior medication will be at Screening only.

^q Nurse visit at home only where approved and with agreement of subjects. Otherwise, the visit procedures will be done onsite by the site staff.

^r Refer to Protocol [Section 3](#) for definition. In case of loss of sustained remission in Part B, the subject must visit the study site for the next scheduled dose of study medication. The Investigator will initiate the escape treatment as appropriate. Refer to [Table 5.2](#) for details.

^s Subjects will be contacted by telephone about every 4 weeks in between the onsite visits.

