6.3.2 Escape treatment

Subjects receiving placebo or half-dose CZP (200mg Q4W) who experience a flare during the Double-Blind Period will escape to full-dose treatment (CZP 200mg Q2W) until the end of that period or for at least 12 weeks, whichever is longer. The escapers need to come back to the site at the timepoint of the escape (Week 0), 2 and 4 weeks after escape (Weeks 2 and 4), and every 12 weeks thereafter until the originally scheduled Week 96.

Subjects escaping from placebo to full-dose CZP (200mg Q2W) will receive a loading dose of CZP (400mg Q2W; 2 injections) at the 3 consecutive visits after the flare. Subjects escaping

from half-dose CZP to full-dose CZP will receive a loading dose of CZP 200mg Q2W at the 3 consecutive visits after the flare. In order to maintain the blind, subjects escaping from half-dose CZP to full-dose CZP will receive a placebo administration and a CZP 200mg administration (a total of 2 injections) at these 3 visits ([Figure 7.1](#)).

Subjects randomized to the CZP full-dose (200mg Q2W) treatment during the Double-Blind Period who qualify for escape will remain on their current treatment allocation. As with subjects escaping from half-dose CZP to full-dose CZP, these subjects will receive a placebo and CZP 200mg injection (a total of 2 injections) at the 3 visits after the flare in order to maintain the blind to the randomized treatment.

After the loading dose (200mg Q2W or 400mg Q2W), all escaped subjects will continue full-dose CZP treatment in an open-label fashion.

The definition of flare is provided in [Section 3](#).

At the Investigator's discretion, the subject may be withdrawn from the study at any time (eg, to receive alternative treatment for the disease).

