- Genomics and proteomics (at Weeks 12, 24, 72, and at Week 96/WD only), if applicable.
- Stool sample will be collected for fecal calprotectin at Week 48 and at Week 96/WD only.
- Blood sample will be collected for serum calprotectin at Week 12, Week 24, Week 72 and Week 96/WD only.
- Concomitant medication

- AEs
- Contact IXRS to obtain next kit numbers.
- Study drug administration (after all other visit assessments are completed and laboratory samples are drawn) (all visits except at Week 96/WD).
- Randomization at Week 48
- Check of sustained remission criteria (all visits except Weeks 2, 4, and Week 96/WD visit)

8.3.2 3 to 5 days prior to Week 48

- Blood samples will be collected for hematology and biochemistry analyses and CRP
- BASDAI
- BASFI
- SF-36
- ASQoL
- EQ-5D
- IBD-Q
- Total spinal pain NRS and nocturnal spinal pain NRS
- PtGADA
- Plasma for CZP concentration and ADAbs
- Plasma for biomarkers
- Genetics
- Blood sample will be collected for serum calprotectin
- AEs

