8.4.2 Home and home nurse visits during Part B

Assessments at these home and nurse visits include:

- Vital signs: pulse rate, systolic and diastolic blood pressures, temperature will be measured. If a subject experiences an AE, respiration rate will be measured in addition (at Week 50, Weeks 54 to 58, 62 to 70, 74 to 82, and 86 to 94 only)

- CRP and PtGADA (at Weeks 50, 56, 64, 68, 76, 80, 88, and 92)
- BASDAI (at Weeks 50, 56, 64, 68, 76, 80, 88, and 92)
- Contact IXRS to report kit number (all Visit at Weeks 50, 54 to 58, 62 to 70, 74 to 82, and 86 to 94)
- Nurse visit at subject home including to perform study medication administration (at Weeks 50, 54, 56, 58, 62, 64, 66, 68, 70, 74, 76, 78, 80, 82, 86, 88, 90, 92, and 94)
- Check of sustained remission criteria (at Weeks 50, 56, 64, 68, 76, 80, 88, and 92)

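### Table 5.1 prompts escape on loss of sustained remission, the rest of the protocol on flare, and the primary rules are silent on escape started without a flare

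*Protocol*

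**What the plan says.** Section 3 defines two states. On remission: "Sustained remission is achieved when a subject has an ASDAS <1.3 at Week 32 or Week 36". A value below 2.1 is accepted at the other of those two visits, and Week 48 must also qualify. All three visits are in Part A. On flare: "A flare occurs when a subject has an ASDAS ≥ 2.1 at 2 consecutive visits or ASDAS >3.5 at any visit during Part B". Section 3 also reserves the term escaper for subjects who meet the flare criteria and cross over to full dose.

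Section 6.3.2 states that subjects on placebo or half-dose "who experience a flare during the Double-Blind Period will escape to full-dose treatment (CZP 200mg Q2W". Sections 5.1.3 and 8.5 and the text that introduces Table 5.2 use the same trigger, and 5.1.3 assigns the flare determination to IXRS.

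Footnote r of Table 5.1 refers to Section 3 for the definition and continues: "In case of loss of sustained remission in Part B, the subject must visit the study site for the next scheduled dose". It then says: "The Investigator will initiate the escape treatment as appropriate", and sends the reader to Table 5.2.

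The scheduled Part B checks carry the remission label. Section 8.4.2 lists: "Check of sustained remission criteria (at Weeks 50, 56, 64, 68, 76, 80, 88, and 92". Section 8.3.1 has the matching onsite entry: "Check of sustained remission criteria (all visits except Weeks 2, 4, and Week 96/WD visit". None of these entries names a flare check.

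Sections 14.3.1 and 14.6 impute a flare in two situations only: withdrawal from Part B, and ASDAS missing at two or more consecutive visits.

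**The concern.** The visit schedule is what sites work from. There, the prompt for the escape visit and for starting escape is loss of a state that Section 3 does not define in Part B. A site could apply the remission cut-off of 1.3 to a Part B value, or act on a single value of 2.1 to 3.5, and so treat as eligible a subject who has not flared. Other sites would wait for the flare criteria.

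The primary endpoint is the proportion without a flare. Escape gives placebo and half-dose subjects full-dose treatment, while full-dose subjects keep their dose. A placebo subject moved to full dose before flaring may never meet the flare criteria and would then count as a success for placebo. The same event would raise the half-dose rate, which also matters for the secondary comparison of full with half dose (Section 3.2).

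**Working it through.** **1. The two prompts side by side**

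| | Footnote r, check row, 8.3.1, 8.4.2 | Sections 3, 5.1.3, 5.2 text, 6.3.2, 8.5 |
|---|---|---|
| Prompt | Loss of sustained remission | Flare |
| Threshold in Part B | None stated | ASDAS at least 2.1 at two consecutive visits, or above 3.5 once |
| Who decides | Investigator, as appropriate | IXRS determines flare |

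If the Part A cut-off were carried into Part B, the prompts would differ for ASDAS from 1.3 to below 2.1 and for a single unconfirmed value of 2.1 to 3.5.

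**2. How the analysis rules treat escape without a flare**

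- Primary (14.3.1, 14.6): flare-free, unless the subject later meets the flare criteria, withdraws, or misses two consecutive ASDAS values.
- Time to flare (14.3.2.2): censored if no flare follows.
- Flared Set (14.1) and the escaper definition (Section 3): not included, since both require a flare.
- MMRM (14.3.2.2): data after the switch are kept, because only post-flare data are set to missing.

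**3. The plan's own power**

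Inputs from 14.8: n = 70 per arm; flare-free 80% (Q2W), 75% (Q4W), 45% (placebo); two-sided 0.05. With p̄ = (p1 + p2)/2, the continuity-corrected normal approximation is

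z = [ |p1 − p2| − 1/n − 1.96·√(2p̄(1 − p̄)/n) ] / √((p1(1 − p1) + p2(1 − p2))/n), power = Φ(z).

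- Q4W vs placebo: (0.30 − 0.0143 − 0.1623)/0.0788 = 1.566, power 94.1%.
- Q2W vs placebo: (0.35 − 0.0143 − 0.1604)/0.0763 = 2.298, power 98.9%.

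The plan states 94% and 98%, so its figures reproduce to within about one point.

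**4. Illustration of early escape**

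Assume that a share f of would-be flarers on placebo and half-dose is escaped before a flare and then stays flare-free, with full dose unchanged. Placebo becomes 0.45 + 0.55f and half-dose 0.75 + 0.25f. The protocol gives no value for f.

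| f | Placebo | Half-dose | Placebo subjects affected (70 × 0.55f) | Power Q2W | Power Q4W |
|---|---|---|---|---|---|
| 0 | 45% | 75% | 0 | 98.9% | 94.1% |
| 10% | 50.5% | 77.5% | 3.9 | 94.6% | 89.3% |
| 20% | 56% | 80% | 7.7 | 82.5% | 82.5% |
| 30% | 61.5% | 82.5% | 11.5 | 60.5% | 73.8% |

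For f = 10%, Q4W: (0.27 − 0.0143 − 0.1590)/0.0779 = 1.242, power 89.3%.

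**The case against.** The best answer is that footnote r is loose wording for flare. What it makes mandatory is a site visit. Escape follows only as appropriate, with a pointer to Table 5.2, whose title covers subjects experiencing a flare. Sections 2.5 and 5.4 list loss of sustained remission among the flare definitions used in earlier studies. IXRS calculates ASDAS, determines flare and allocates kits, and the protocol describes no route to escape supply without a flare. Under the body text, an early switch would be a protocol deviation, reviewed before unblinding, with a per-protocol sensitivity analysis of the primary endpoint available. These points stand as reasons to expect early escape to be uncommon. They do not remove the conflict: no passage says that footnote r means flare, and the primary rules set out in the protocol do not address the case.

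Three stronger readings are tempting but not supported:

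- That ASDAS of 1.3 to below 2.1 is itself an escape trigger. No Part B threshold for loss of remission is stated, so this extends a Part A definition.
- That a modest rate of early escape on placebo would cut half-dose power to 83% or lower. That follows from placebo at 50% with half-dose held at 75%. Half-dose subjects also escape to full dose, and moving both arms gives 89.3% at a placebo rate of 50.5%.
- That omitting the check at Week 96 affects the primary endpoint. Table 5.1 schedules CRP, BASDAI and the patient's global assessment at Week 96, so ASDAS can be calculated and the subject classified.

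**Conclusion.** The inconsistency is real and sits in the current operational text. Its effect on the primary endpoint is conditional: a subject must be escaped without a flare and then stay flare-free, in the study, and without two consecutive missing ASDAS values. Where that happens, the bias is toward no difference from placebo, so it does not threaten a false claim of superiority. It would also raise the half-dose rate relative to full dose.

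The size cannot be read from the protocol. The 10% case (power about 95% for Q2W and 89% for Q4W) is illustrative, and it assumes that every early switch involves a subject who would have flared and then does not. This is a consistency correction worth making, not a defect that must be cured before the primary analysis can be relied on.

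**What to change.** Reconcile footnote r, the check row of Table 5.1 and the matching entries in 8.3.1 and 8.4.2 with Sections 3, 5.1.3 and 6.3.2, so that one escape trigger is stated throughout. Which trigger is a clinical decision and is not judged here.

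In 14.3.1, 14.6 and the time-to-flare paragraph of 14.3.2.2, add that a subject who starts escape treatment without having met the flare criteria is counted as flared at the first escape dose. This follows the nonresponse principle already used for withdrawals. It leaves the 80/75/45% assumptions, and so the planned power, as they are when the switched subjects are would-be flarers.

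The cost is wording in one footnote, one row label and two list entries, plus one analysis sentence used in three places. IXRS already calculates ASDAS, so no new data are needed.

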4.4 Safety variables

Safety variables to be assessed are AEs, physical examination, vital sign measurements, chest x-ray, and measurements of laboratory parameters (hematology, biochemistry, and urinalysis).

Adverse events will be solicited at every visit, and recorded and coded according to the latest version of the Medical Dictionary for Regulatory Activities® criteria used at UCB at the time of analysis.

Physical examination findings will be recorded in the electronic Case Report Form (eCRF) only at Screening. Clinically relevant changes in subsequent physical examinations will be recorded as AEs.

Clinical laboratory values (hematology, biochemistry, and urinalysis) will be collected and assessed at Screening, Baseline, at Weeks 12, 24, 32, 36, and every 12 weeks thereafter through to study Week 96/WD Visit and at the SFU Visit 10 weeks after the last dose of study medication. C-reactive protein values will be collected and assessed at Screening, Baseline, Weeks 2, 4, 12, 24, 32, 36, 3 to 5 days prior to Week 48, Week 50, Week 52, and every 4 weeks thereafter through to study Week 96/WD Visit. For escapers, different schedules for clinical laboratory values and CRP apply after start of the escape treatment (refer to [Table 5.2](#)).

At Screening, Week 48, and Week 96, all subjects will have an IGRA test (QuantiFERON TB GOLD In Tube test or another WHO-validated IGRA test such as Elispot, if QuantiFERON TB GOLD In Tube test is not available locally). A chest x-ray (or, if done, computed axial tomography of the chest) at Screening (or up to 3 months prior to Screening) must be read and reported consistent with standard clinical reporting practice by an experienced TB specialist, radiologist or a pulmonologist, who is specifically required to look for signs of active TB or signs of past/inactive TB infection. The official report of the imaging must specifically indicate the absence of findings suggestive of current active TB or prior inactive TB. In addition to a physical examination done intermittently throughout the study, subjects will be evaluated at Screening, Baseline, and every 12 weeks thereafter, including the Week 96/WD Visit, for signs and symptoms of latent or active TB infection and risk factors for exposure to TB using the TB questionnaire.

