Swollen and tender joint counts		X	X	X		X		X			X			X			X		X		X		X		X	
Patient's Global Assessment of Disease Activity ^f	X	X	X	X		X		X		X		X		X	X	X	X	X	X	X	X	X	X	X	X	
Physician's Global Assessment of Disease Activity		X				X		X			X			X			X		X		X		X		X	
Work Productivity		X	X		X		X			X			X			X		X		X		X		X		X

Table 5.1: Schedule of study assessments for all subjects completing Part A and Part B

Study Period	PART A														PART B										4			
	1 (Screening)	0	2	4	6 to 10 H	12	14 to 22 H	24	26 to 30 H	32	34 H	36	38 to 46 H	3-5 days prior to W48 visit ^a	48	50 HN	52	54 to 58 HN	60	62 to 70 HN	72	74 to 82 HN	84	86 to 94 HN	96/ WD	SFU ^b		
Week (W)	-5 to -1 weeks																											
Protocol Activity																												
Survey																												
Resources utilization ^c		X			X		X			X					X			X		X		X		X		X		
CZP plasma concentration/ ADAb		X		X		X		X							X				X		X		X		X		X	
Biomarker		X		X		X		X							X				X		X		X		X		X	
Genetics		X													X													
Genomics/ proteomics		X			X		X								X												X	
Prior and Concomitant medication ^p	X	X	X		X		X		X		X				X		X		X		X		X		X		X	
AEs		X	X	X		X		X		X		X		X	X	X	X	X	X	X	X	X	X	X	X	X		
IXRS	X	X	X		X		X		X		X				X	X	X	X	X	X	X	X	X	X	X	X		
Study drug sc onsite		X	X	X		X		X		X		X			X		X		X		X		X					
Study drug sc self-inj. at home					X		X		X		X		X															
Randomization															X													
Nurse visit at subj. home (incl. study drug sc inj.) ^q																X		X		X		X		X		X		

Table 5.1: Schedule of study assessments for all subjects completing Part A and Part B

Study Period	PART A														PART B											
	1 (Screening)	2 (Open-Label)													3 (Double-Blind)										4	
Week (W)	-5 to -1 weeks	0	2	4	6 to 10 H	12	14 to 22 H	24	26 to 30 H	32	34 H	36	38 to 46 H	3-5 days prior to W48 visit ^a	48	50 HN	52	54 to 58 HN	60	62 to 70 HN	72	74 to 82 HN	84	86 to 94 HN	96/WD	SFU ^b
Protocol Activity																										
Check of sustained remission criteria ^c					X		X		X		X				X	X	X	X	X	X	X	X	X	X		
Telephone Contact ^d				X		X		X					X													

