Concomitant medication	X	X	X			X	
AEs	X	X	X			X	
IXRS	X	X	X	X		X	X
Study drug sc onsite	X	X	X			X	
Study drug sc self-inj. at home					X		X
Telephone Contact ^k					X		X

Abs=antibodies; ADAb=anti-CZP antibody; AEs=adverse events; AS=ankylosing spondylitis; AsQoL=Ankylosing Spondylitis Quality of Life; BASDAI=Bath Ankylosing Spondylitis Disease Activity Index; BASFI=Bath Ankylosing Spondylitis Functional Index; BASMI=Bath Ankylosing Spondylitis Metrology Index; CRP=C-reactive protein; CZP=certolizumab pegol; EQ-5D=EuroQoL Health Status Questionnaire; H=home, no site visit; HN=home nurse visit at subjects home; IBD=Inflammatory bowel disease; IXRS=Interactive Voice or Web Response System; MASES=Maastricht Ankylosis Spondylitis Enthesitis Score; MRI=magnetic resonance imaging; PE=physical exam; sc=subcutaneously; SF-36=Short-Form 36-item Health Survey; TB=tuberculosis; W=Week

^a HN Q4W only for obtaining blood sample (CRP) and electronic patient reported outcome (ePRO) data as indicated

^b Schedule onsite visit every 12 weeks until Week 96 of regular visit schedule is reached. For example, at Weeks 74 and 86, if start of escape treatment is at Week 62 (=Escape Week 0). At Week 96 and SFU, perform assessments as described in [Table 5.1](#). For subjects experiencing a flare at/after Week 82, escape treatment should be provided for 12 weeks and the subject invited for the final assessment visit (as laid down for Week 96) 2 weeks later

^c Until 2 weeks before Week 96 of regular visit schedule is reached

^d Pulse rate, systolic and diastolic blood pressures, temperature, and respiration rate are to be measured at Screening and Baseline, thereafter pulse rate, systolic and diastolic blood pressures and temperature are to be measured. If a subject experiences an AE, respiration rate will be measured in addition

^e To be assessed as indicated and from Week 52 onwards every 4 weeks only

^f To be assessed every 4 weeks only (Weeks 8, 12, 16, 20, 24, ... up to Week 96)

^g To be assessed at escape Weeks 0 and 12 only

^h To be performed at escape Weeks 0 and 12 only and at final assessment visit at Week 96, if the last MRI was done at least 12 weeks prior to Week 96. Magnetic resonance imaging is to be performed within a ± 2 weeks time window.

[figure not shown]
ⁱ Occiput to wall distance; chest expansion; and BASMI, which includes modified Schober test, lateral spinal flexion, cervical rotation, tragus to wall distance, and maximal intermalleolar distance

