14.4 Planned safety and other analyses

14.4.1 Safety analyses

The frequency of all AEs by study period (Part A and Part B) will be presented separately by System Organ Class, high-level term, and preferred term and for Part B by each treatment group. The data will be displayed as number of subjects experiencing the AEs, percentage of subjects, and number of AEs. Data will also be corrected for exposure by 100 patient years.

Laboratory evaluations and vital signs will be analyzed over time in the SS and SSB for observed cases and at the end of treatment.

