14.8 Determination of sample size

It is anticipated that approximately 210 subjects will be randomized in a 1:1:1 ratio to the CZP 200mg Q2W, CZP 200mg Q4W, and placebo treatment groups. The primary efficacy analysis is based on the proportion of subjects who do not experience a flare during Part B of the study. The proportion of subjects who do not experience a flare during Part B is assumed to be 80%, 75%, and 45% for the CZP 200mg Q2W, CZP 200mg Q4W, and placebo treatment groups, respectively. Given these assumptions, a sample size of 70 subjects per group provides 98% power to detect a significant difference between the CZP 200mg Q2W dose and placebo and 94% power to detect a significant difference between the CZP 200mg Q4W dose and placebo using a 2-sided significance level of 0.05.

Given that subjects enter Part B only if they have achieved sustained remission in Part A, it is necessary to estimate the number of subjects needed to enroll in Part A. It is assumed that approximately 28% of subjects enrolled in Part A will achieve sustained remission and qualify for Part B. This means that about 750 subjects will be enrolled in Part A in order to have 210 subjects who are randomized into Part B. Subject response to treatment will be evaluated on an ongoing basis as subjects enroll in Part A, and the number of subjects enrolled will be adapted accordingly in order to achieve 210 subjects randomized to Part B.

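### Adverse event solicitation in Part B is scheduled inconsistently and becomes sparser after flare, so scheduled prompts can differ by arm

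*Protocol*

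**What the plan says.** **Before flare.** The AE row of Table 5.1 is marked in every Part B column, home nurse columns included. It carries no footnote limiting it to every fourth week, unlike CRP, BASDAI and the patient global assessment. With the dosing visits every 2 weeks, that is a 2-weekly prompt. Section 8.4.2 opens its list with "Assessments at these home and nurse visits include" and names no AE item, although it adds respiration rate when a subject has an AE.

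**After flare.** Table 5.2 marks AEs at Escape Weeks 0, 2, 4, 12 and every 12 weeks thereafter. Both home columns are blank. Footnote a says "HN Q4W only for obtaining blood sample (CRP) and electronic patient reported outcome (ePRO) data as indicated". Footnote k schedules telephone contact about every 4 weeks without stating its content. Section 8.5 lists AEs with no weeks attached, and its lead-in refers the timing to Table 5.2.

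**General rule.** Section 4.4: "Adverse events will be solicited at every visit". Section 12.1.2 likewise asks for a general prompt at each study visit and accepts spontaneous reports.

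**Analysis.** Section 14.4.1 presents Part B AEs by treatment group and adds: "Data will also be corrected for exposure by 100 patient years". It does not say whether events and exposure after escape stay with the randomised arm. Section 14.1 defines a Part B Full-Dose Set containing everyone who received Q2W dosing in Part B, escape treatment included.

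**The concern.** The switch from one schedule to the other is triggered by flare, which is the primary efficacy outcome and is expected to differ by arm. If the tables are followed as written, a randomised comparison of AE frequencies mixes subjects asked every 2 weeks with subjects asked after gaps of 8 and then up to 12 weeks. The arm with most flares has most of the sparsely prompted time.

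Events that are mild and short, and so poorly recalled, are the ones exposed. Serious events are less affected. The sparse period also follows re-initiation of full-dose treatment, and Section 2.5 says the study will provide safety data on retreatment. Because the general rules, the two tables and the procedure lists disagree, sites may also differ in what they do.

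**Working it through.** The protocol states no figure for AE ascertainment, so the check counts scheduled prompts.

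**Inputs**
- Section 14.8: non-flare proportions are "assumed to be 80%, 75%, and 45% for the CZP 200mg Q2W, CZP 200mg Q4W, and placebo treatment groups, respectively", so flare rates are 20%, 25% and 55%.
- Section 14.8: 70 subjects per arm.
- AE prompts: Tables 5.1 and 5.2.
- Week 62 as an example start of escape: Table 5.2, footnote b.

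The planning figures hang together. With these rates and 70 per arm, a continuity-corrected two-sided 0.05 comparison gives 98.9% and 94.1% power, against the stated 98% and 94%. Without the correction it gives 99.4% and 96.0%.

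**Expected flares.** Full-dose 70 × 0.20 = 14; half-dose 70 × 0.25 = 17.5; placebo 70 × 0.55 = 38.5. The total is 70, and placebo's share is 38.5/70 = 55%.

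**One escaper, Week 62.** Table 5.2 gives prompts at Weeks 62, 64, 66, 74, 86 and 96: six, with gaps of 2, 2, 8, 12 and 10 weeks. Table 5.1 gives 18 over the same weeks. Weeks 48 to 60 add 7, so the subject has 7 + 6 = 13, against 25 for a subject who never flares.

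**If every escape is at Week 62** (Week 48 counted)
- Placebo: 0.45 × 25 + 0.55 × 13 = 18.4
- Half-dose: 0.75 × 25 + 0.25 × 13 = 22.0
- Full-dose: 0.80 × 25 + 0.20 × 13 = 22.6
- 18.4/22.6 = 0.81, so 19% fewer on placebo.

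**If flares are spread evenly** over Weeks 52, 56, ..., 92, with escape 2 weeks later and prompts counted after Week 48 up to Week 96: an unflared subject has 24. The 11 possible flare weeks give 9, 11, 12, 14, 16, 17, 19, 21, 21, 23 and 24, so the mean is 187/11 = 17.0.
- Placebo: 0.45 × 24 + 0.55 × 17 = 20.15
- Half-dose: 0.75 × 24 + 0.25 × 17 = 22.25
- Full-dose: 0.80 × 24 + 0.20 × 17 = 22.6
- 20.15/22.6 = 0.89, so about 11% fewer on placebo.

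Mean escape is then at Week 74. Post-escape time is (96 − 74)/48 = 46% of a flared subject's Part B, or about 25%, 11% and 9% of arm time (placebo, half-dose, full-dose).

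**If the 4-weekly contacts after flare also prompt for AEs.** The flared mean becomes 19.7, and the arm means are 21.6, 22.9 and 23.1 (placebo, half-dose, full-dose). 21.6/23.1 = 0.935, about 6.5% fewer on placebo. For escape at Week 62 there are 11 prompts with a longest gap of 4 weeks.

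**If Section 8.4.2 is followed literally**, so that unflared subjects are prompted only at onsite visits: after Week 48 an unflared subject has 5 (Weeks 52, 60, 72, 84, 96) and a flared subject averages 84/11 = 7.6. The arm means are 6.5, 5.7 and 5.5. Placebo now has the most, about 17% more than full-dose (6.45/5.53).

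**The case against.** A reader might infer that the placebo arm's AE rates will be biased downwards by about a fifth. The protocol does not support that, for five reasons.

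- **Direction.** It depends on which text a site follows. Section 8.4.2 taken literally reverses it.
- **Attribution.** The imbalance reaches the by-arm rates only if events and exposure after escape are counted in the randomised arm. Section 14.4.1 leaves this open, and a SAP may properly settle it. If counting stopped at escape, Table 5.1 would apply equally to all arms.
- **General rules.** Sections 4.4 and 12.1.2 already require a prompt at every visit. Footnote a can be read as saying only when a nurse is needed for subjects who self-inject. A 12-week silence is therefore the literal table reading and not the only one, and it starts only after Escape Week 12.
- **Prompts are not events.** All AEs must be reported, spontaneous reports are taken, and later visits ask about the interval.
- **Familiar pattern.** Part A also leaves AEs blank at self-injection weeks, with onsite visits up to 12 weeks apart.

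All of this limits the size and certainty of the effect, but it does not remove the point. Section 8.5 sends sites to Table 5.2 for timing, so the general rules do not clearly override the blank cells. Part A has one arm, so sparse prompting there distorts no randomised comparison. A cut at escape would still leave the Full-Dose Set combining full-dose subjects who never flared, prompted 2-weekly, with escapers prompted far less often.

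**Conclusion.** The point holds as an inconsistency with a possible effect on the safety comparison; it does not show a bias of known size or sign. Tables 5.1 and 5.2 set different solicitation intervals for unflared and flared subjects. Sections 4.4, 8.4.2, 8.5 and 12.1.2 do not agree on which applies.

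On the table reading, and with post-escape time kept in the randomised arm, placebo has about 11% fewer scheduled prompts than full-dose. The 19% figure needs every escape to fall at Week 62. The 11% assumes flares spread evenly over the 4-weekly ASDAS visits, follow-up to Week 96, and that every subject planned as a flare escapes. Section 14.3.1 also counts withdrawals as flares, so the number who actually escape could be lower.

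The likely consequence is weaker recall of non-serious AEs, and the protocol gives no figure for it. The correction is cheap and should be made.

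**What to change.** 1. In Table 5.2 and Section 8.5, add an AE prompt to the nurse and telephone contacts that already occur about every 4 weeks, and delete the word *only* from footnote a.
2. Add AEs to Section 8.4.2, so that it agrees with Table 5.1 and Section 4.4.
3. State in Section 14.4.1 how AEs and exposure after escape are attributed, in agreement with the SAP.

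Step 1 shortens the longest gap from 12 weeks to 4 and reduces the placebo shortfall from about 11% to about 6.5% on the even-spread count. It does not remove it, because unflared subjects would still be asked every 2 weeks, so step 3 is needed as well. Concomitant medication need not be added for parity, because Table 5.1 does not mark it at home nurse visits either.

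The cost is amendment wording, an eCRF prompt at contacts already planned, and a few more minor AEs to record.
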